8.5.2 Information Required for Reporting Purposes

- Description of compliant
- Reporter identification (eg, subject, investigator, site, etc.)
- Reporter contact information (eg, address, phone number, e-mail address)
- ID of material (product/compound name, coding)
- Clinical protocol reference (number and/or trial name)
- Dosage form/strength (if known)
- Pictures (if available)
- Availability for return

8.5.3 Return Process

Indicate during the report of the PQC if the complaint sample is available for return. If complaint sample is available for return, return it in the product retrieval package, which will be provided by the sponsor.

It must be documented in the site accountability record that a complaint sample for a dispensed kit has been forwarded to the sponsor for complaint investigation.

8.5.4 Assessment/Evaluation

Assessment and evaluation of PQCs will be handled by the sponsor.

9 Records Management

9.1 Source Documents

Source documents are defined as the results of original observations and activities of a clinical investigation. Source documents will include but are not limited to progress

Protocol 31-14-204

notes, electronic data, screening logs, and recorded data from automated instruments. All source documents pertaining to this trial will be maintained by the investigators and made available for direct inspection by authorized persons.

Investigator(s)/institution(s) will permit trial-related monitoring, audits, IRB/IEC review, and regulatory inspection(s) by providing direct access to source data/documents by authorized persons as defined in the ICF. In all cases, subject confidentiality must be maintained in accordance with local regulatory requirements.

9.2 Data Collection

Source document and source data will be captured electronically in this trial, and will meet the same fundamental elements of data quality (eg, attributable, legible, contemporaneous, original, and accurate) as paper records. These data will be collected into a system that is fully validated. Changes to the data will be captured by an automatic audit trail.

The trial site will be given a tablet to directly record subject data and clinical observations on electronic forms. Designated trial site staff will not be given access to the system until they have been appropriately trained. Information to be originally captured and reviewed electronically shall include details of the subject visit and the protocol-required assessments performed as a part of these visits, medical history, AEs, and concomitant medications. Because this trial is using an electronic source record as the original point of data capture, there is no additional data entry step for the site for data collected directly into the application - rather, the electronic source record directly populates the trial database.

Some data may be captured via paper and then entered into the eSource system. These and any other data treated in this manner will be source data verified by the trial clinical research associate, and the location of the source data (ie, eSource, paper, or a local electronic system) will be documented before the trial start. Any changes to information in paper source documents will be initialed and dated on the day the change is made by a trial site staff member authorized to make the change. Changes will be made by striking a single line through erroneous data (so as not to obliterate the original data), and clearly entering the correct data (eg, ~~wrong data~~ right data). If the reason for the change is not apparent, a brief explanation for the change will be written in the source documentation by the clinician.

Protocol 31-14-204

Another exception will be safety laboratory data, where the official source documentation will be considered the report issued by the analyzing laboratory.

Remote monitoring of the original electronic source record will take place, however on-site monitoring inspections will continue to take place in order to review data entry source documentation directly captured on paper and transcribed into the system, to ensure protocol adherence, to assess site operational capabilities and to perform other monitoring activities that cannot be performed remotely.

At the end of the trial, the investigator must certify that the data entered into the eSource application are complete and accurate. After database lock, the investigator will receive an electronic copy of the subject data.

9.3 File Management at the Trial Site

The investigator will ensure that the trial site file is maintained in accordance with Section 8 of the ICH GCP Guideline E6 and as required by applicable local regulations. The investigator/institution will take measures to prevent accidental or premature destruction of these documents.

9.4 Records Retention at the Trial Site

Regulatory requirements for the archival of records for this trial necessitate that participating investigators maintain detailed clinical data for the longest of the following 3 periods:

- A period of at least 2 years after the date on which approval to market the drug is obtained (or if IMP development is discontinued, the date regulatory authorities were notified of discontinuation); OR
- A period of at least 3 years after the sponsor notifies the investigator that the final report has been filed with regulatory authorities.
- Longer, region-specific storage requirements, if applicable.

The investigator must not dispose of any records relevant to this trial without either (1) written permission from the sponsor or (2) provision of an opportunity for sponsor to collect such records. The investigator will be responsible to maintain adequate and accurate electronic or hard copy source documents of all observations and data generated during this trial including any data clarification forms received from the sponsor. Such documentation is subject to inspection by the sponsor and relevant regulatory authorities. If the investigator withdraws from the trial (eg, due to relocation or retirement), all trial-related records should be transferred to a mutually agreed-upon designee within a

Protocol 31-14-204

sponsor-specified timeframe. Notice of such transfer will be given to the sponsor in writing.

10 Quality Control and Quality Assurance

10.1 Monitoring

The sponsor has ethical, legal, and scientific obligations to follow this trial in accordance with established research principles, the ICH E6 GCP: Consolidated Guidance, and applicable regulatory requirements and local laws. As part of a concerted effort to fulfill these obligations (maintain current personal knowledge of the progress of the trial), the sponsor's monitors will visit the site during the trial, as well as communicate frequently via telephone, e-mail, and written communications. In addition, all investigators and clinical site personnel will undergo initial and ongoing training for this particular trial, and this training will be clearly documented.

10.2 Auditing

The sponsor's Quality Assurance Unit (or representative) may conduct trial site audits. Audits will include, but are not limited to, IMP supply, presence of required documents, the informed consent process, and comparison of eSource with source documents. The investigator agrees to participate with audits.

Regulatory authorities may inspect the investigator site during or after the trial. The investigator will cooperate with such inspections and will contact the sponsor immediately if such an inspection occurs.

11 Ethics and Responsibility

This trial must be conducted in compliance with the protocol, FDA regulations, ICH GCP Guideline (E6), international ethical principles derived from the Declaration of Helsinki and Council for International Organizations of Medical Science (CIOMS) guidelines, and applicable local laws and regulations. Each trial site will seek approval/favorable opinion by an IRB or IEC according to regional requirements, and the investigator will provide that documentation to the sponsor. The IRB/IEC will evaluate the ethical, scientific and medical appropriateness of the trial. Further, in preparing and using screens in eSource, the investigator, sub-investigator and their staff will take measures to ensure adequate

Protocol 31-14-204

care in protecting subject privacy. To this end, a subject number and subject identification code will be used to identify each subject.

Financial aspects, subject insurance and the publication policy for the trial will be documented in the agreement between the sponsor and the investigator.

12 Confidentiality

All information generated in this trial will be considered confidential and will not be disclosed to anyone not directly concerned with the trial without the sponsor's prior written permission. Subject confidentiality requirements of the region(s) where the trial is conducted will be met. However, authorized regulatory officials and sponsor personnel (or their representatives) may be allowed full access to inspect and copy the records, consistent with local requirements. All IMPs, subject bodily fluids, and/or other materials collected shall be used solely in accordance with this protocol, unless otherwise agreed to in writing by the sponsor.

Subjects will be identified only by unique subject numbers in eSource. If further subject identification is required, subjects' full names may be made known to a regulatory agency or other authorized officials if necessary, subject to local regulations.

13 Amendment Policy

The investigator will not make any changes to this protocol without the sponsor's prior written consent and subsequent approval/favorable opinion by the IRB/IEC. Any permanent change to the protocol, whether an overall change or a change for specific trial site(s), must be handled as a protocol amendment. Any amendment will be written by the sponsor. Each amendment will be submitted to the IRB/IEC, as required by local regulations. Except for "administrative" or "non-substantial" amendments, investigators will wait for IRB/IEC approval/favorable opinion of the amended protocol before implementing the change(s). Administrative amendments are defined as having no effect on the safety of subjects, conduct or management of the trial, trial design, or the quality or safety of IMP(s) used in the trial. A protocol change intended to eliminate an apparent immediate hazard to subjects should be implemented immediately after agreement by the sponsor and investigator, followed by IRB/IEC notification within local applicable timelines. The sponsor will submit protocol amendments to the applicable regulatory agencies within local applicable timelines.

Protocol 31-14-204

When the IRB/IEC, investigators, and/or the sponsor conclude that the protocol amendment substantially alters the trial design and/or increases the potential risk to the subject, the currently approved written ICF will require similar modification. In such cases, after approval/favorable opinion of the new ICF by the IRB/IEC, repeat written informed consent will be obtained from subjects enrolled in the trial before expecting continued participation and before the amendment-specified changes in the trial are implemented.

14 Publication Authorship Requirements

Authorship for any Otsuka-sponsored publications resulting from the conduct of this trial will be based on International Committee of Medical Journal Editors (ICMJE) authorship criteria (<http://www.icmje.org/recommendations>). According to ICMJE guidelines, one may be considered an author only if the following criteria are met:

- 1) Substantial contributions to the conception or design of the work; or the acquisition, analysis, or interpretation of data for the work; AND

Appendix 1 Criteria for Identifying Vital Signs of Potential Clinical Relevance

Variable	Criterion Value ^a	Change Relative to Baseline ^a
Heart Rate ^b	> 120 bpm < 50 bpm	≥ 15 bpm increase ≥ 15 bpm decrease
Systolic Blood Pressure ^b	> 180 mmHg < 90 mmHg	≥ 20 mmHg increase ≥ 20 mmHg decrease
Diastolic Blood Pressure ^b	> 105 mmHg < 50 mmHg	≥ 15 mmHg increase ≥ 15 mmHg decrease
Weight	-	≥ 7% increase ≥ 7% decrease

^aIn order to be identified as potentially clinically relevant, an on-treatment value must meet the “Criterion Value” and also represent a change from the subject’s baseline value of at least the magnitude shown in the “Change Relative to Baseline” column.

^bAs defined in “Supplementary Suggestions for Preparing an Integrated Summary of Safety Information in an Original NDA Submission and for Organizing Information in Periodic Safety Updates,” FDA Division of Neuropharmacological Drug Products draft (2/27/87).

Protocol 31-14-204

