^bBenzotropine (up to 4 mg/day) is not to be administered 12 hours prior to rating scales. Benzodiazepines (up to 3 mg/day lorazepam equivalents) are not to be administered 4 hours prior to rating scales.

^cVital signs include systolic and diastolic blood pressure and heart rate and will be performed at all in-clinic visits. Orthostatic assessments of blood pressure and heart rate will be made after the subject has been sitting for at least 5 minutes and again after the subject has been standing for approximately 2 minutes, but not more than 3 minutes. If a remote visit is converted to an in-clinic visit, vital signs will be recorded. Vital signs will not be collected for remote visits that are not converted to occur in-clinic.

^dA standard 12-lead ECG will be performed at rest after the subject has been lying down for approximately 5 minutes. ECGs will be evaluated at the investigational site to monitor safety.

^eSubjects should fast for a minimum of 8 hours prior to blood draws for all laboratory assessments.

^fIf the observed TSH level is outside of the normal range, tests of triiodothyronine (T3) and thyroxine (T4) levels will be assessed.

^gUrine pregnancy tests can be performed at any point during the trial if pregnancy is suspected. All positive urine pregnancy test results must be confirmed by a serum test. Treated subjects with a positive urine and serum pregnancy test must discontinue treatment, be withdrawn from the trial, and an IRE form should be completed.

Protocol 31-14-204

^hAbstinence will be permitted if it is confirmed and documented at every trial visit.

ⁱA urine drug screen and a urine blood test can be conducted at any time during the trial at the discretion of the investigator. Subjects who have 2 positive drug screens for any drug of abuse (with the exception of caffeine, nicotine, or prescribed psychostimulants for ADHD) at any time during the trial must be discontinued.

^jAdverse events will be recorded starting at the time the ICF/IAF is signed.

^kAll prescription and nonprescription medications taken during the trial will be recorded as concomitant medications.

Protocol 31-14-204

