3.7.3.3.2 Vital Signs

Vital sign measurements will include systolic and diastolic blood pressure and heart rate and will be performed at all in-clinic visits. If a remote visit is converted to an in-clinic visit, vital signs will be recorded. Vital signs will not be collected for remote visits that are not converted to occur in-clinic.

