7.6.3 Physical Examination, Vital Signs, Body Weight, and Waist Circumference Data

The incidence of potentially clinically relevant vital sign abnormalities and body weight change will be reported for the open-label stabilization phase and by treatment group for the double-blind randomized withdrawal phase with the safety samples appropriate to each phase. Vital sign parameters, body weight, and waist circumference will also be evaluated by their changes from trial baseline for the Open-label Safety Sample and by change from randomization baseline for each treatment group for the Randomized Safety Sample. The BMI values will be calculated based on height and weight measurements and its results will be summarized by change from baseline similarly to body weight. Physical examination data will be listed.

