MODIFICATIONS TO PROTOCOL:

- Definition of cycle length for long-acting (depot) neuroleptics added in Section 3.1, Section 3.7.1.1, and Section 4.1.
- Inclusion of C-SSRS added to occur at Week 3 in Schedule of Assessments (Table 3.7-1) and Section 3.7.1.5.
- Inclusion of vital signs at visits 3, 6, 10, 14 and 18 to the Schedule of Assessments (Table 3.7-1).
- Inclusion of vital signs visits at Weeks 3, 6, and 10 to the Schedule of Assessments (Table 3.7-2).
- Revision of footnotes in Schedule of Assessments (Tables 3.7-1 and 3.7-2), Section 3.7.1.4, Section 3.7.1.5, and Section 3.7.1.7 revised to add that if a remote visit is converted to an in-clinic visit, vital signs will be recorded. Vital signs will not be collected for remote visits that are not converted to occur in-clinic.
- Section 3.7.1.4 revised to include Weeks 14 (± 3 days) and 18 (± 3 days) for the procedures of vital signs, IMP dispensing, and drug accountability to occur.
- Section 3.7.1.4. procedures for psychotropic therapy, YGTSS and CGI-TS, documentation of birth control methods, and stability assessments revised to include “at all open-label visits EXCEPT for Week 3”.
- Section 3.7.1.5 orthostatic assessment instructions added.
- Section 3.7.1.6.1 randomization procedures updated to clarify subjects should be dispensed IMP and administered the first dose while in the clinical “unless evening dose is preferred”.
- The SAS, BARS, and AIMS administer dates corrected in Section 3.7.1.7 to match the Schedule of Assessments and be performed at Week 1 (± 2 days).
- “with direct patient visualization (except for open-label Week 3 which does not require direct patient visualization),” added to the text surrounding telephone visits for Section 3.1 Trial Design, Section 3.7.1 Trial Procedures, footnote under Schedule of Assessments (Table 3.7-1), and Section 3.7.1.4. Footnote under Schedule of Assessments (Table 3.7-2) and Section 3.7.1.4 added “with direct patient visualization”.
- Correction of minor wording and formatting issues.

Protocol 31-14-204

ADDITIONAL RISK TO THE SUBJECT:

There is no additional risk to the subjects.

A complete redline version of this administrative change showing all changes from the previous version of the protocol will be produced and will be available upon final approval of this administrative change.

Protocol 31-14-204

Agreement

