Appendix 2 Criteria for Identifying Vital Signs of Potential Clinical Relevance

Variable	Criterion Value^a	Change Relative to Baseline^a
Heart Rate ^b	> 120 bpm < 50 bpm	≥ 15 bpm increase ≥ 15 bpm decrease
Systolic Blood Pressure ^b	> 180 mmHg < 90 mmHg	≥ 20 mmHg increase ≥ 20 mmHg decrease
Diastolic Blood Pressure ^b	> 105 mmHg < 50 mmHg	≥ 15 mmHg increase ≥ 15 mmHg decrease
Weight	-	≥ 7% increase ≥ 7% decrease

^a In order to be identified as potentially clinically relevant, an on-treatment value must meet the “Criterion Value” and also represent a change from the subject’s baseline value of at least the magnitude shown in the “Change Relative to Baseline” column.

^b As defined in “Supplementary Suggestions for Preparing an Integrated Summary of Safety Information in an Original NDA Submission and for Organizing Information in Periodic Safety Updates,” FDA Division of Neuropharmacological Drug Products draft (2/27/87).

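### Sitting and standing vital signs are collected as an orthostatic assessment, but no criterion, analysis or visible planned table uses the sitting-to-standing change, so a large fall on standing can go uncounted

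*Protocol*

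**What the plan says.** **Collection.** Protocol 3.7.3.3.2: "Vital sign measurements will include systolic and diastolic blood pressure and heart rate and will be performed at all in-clinic visits". The footnotes to both schedules of assessments (Table 3.7-1, note j; Table 3.7-2, note c) set the procedure: "Orthostatic assessments of blood pressure and heart rate will be made after the subject has been sitting for at least 5 minutes". A second set of readings follows once the child has stood for about two, and at most three, minutes. Sections 3.7.1.1 to 3.7.1.8 repeat it visit by visit. The change log for Administrative Change 2 suggests that the pairing is deliberate: "Section 3.7.1.5 orthostatic assessment instructions added".

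**Criteria.** Protocol Appendix 1 has rows for heart rate, systolic pressure, diastolic pressure and weight only. The systolic limits are "> 180 mmHg < 90 mmHg". For blood pressure and heart rate, a value must pass its limit "and also represent a change from the subject’s baseline value of at least the magnitude shown". SAP Appendix 2, "Criteria for Identifying Vital Signs of Potential Clinical Relevance", carries the same rows and the same two-part rule. Neither appendix names a body position.

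**Analysis.** Protocol 7.6.3 plans the incidence of flagged values and adds: "Vital sign parameters, body weight, and waist circumference will also be evaluated by their changes from trial baseline for the Open-label Safety Sample", with change from randomization baseline for the randomized sample. SAP 9.4 plans the same two summaries and gives the blood pressure positions as supine and sitting. The visible vital-sign tables and listing in SAP Appendix 4 are mean change from baseline (CT-11.1.1, CT-17.1.1), incidence of flagged values (CT-11.2, CT-17.2) and a by-subject listing of flagged values (CT-11.3.1). None is described as orthostatic.

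**The concern.** A sitting reading followed by a standing reading is taken in order to see the difference between them at that visit. The plan never forms that difference. It compares each reading with a fixed limit and with a baseline value, and both comparisons can look unremarkable while the pressure drops sharply on standing.

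SAP 9.4 makes this worse. It names a position the protocol does not measure for blood pressure and omits one that it does. As written, sitting is the only position the two documents share, so the standing half of each pair has no stated place in the analysis. SAP 9.4 also keeps the last repeat within a trial week for mean change, without saying that positions are kept apart.

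Safety and tolerability is the trial's secondary objective. Early termination reduced the efficacy analysis to descriptive statistics, but the safety tables remain, and these are the tables in which an orthostatic signal would be sought.

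**Working it through.** The plan states no figure on this point, so there is nothing to reproduce. The check applies the Appendix 1 rule to assumed readings, because the documents give no patient values.

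**Rule (Protocol Appendix 1; SAP Appendix 2 is the same).** A flag needs both parts, in the same direction.

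| Measure | Limit | Change from baseline |
|---|---|---|
| Systolic | > 180 or < 90 mmHg | at least 20 mmHg |
| Diastolic | > 105 or < 50 mmHg | at least 15 mmHg |
| Heart rate | > 120 or < 50 bpm | at least 15 bpm |

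**Step 1: one child.** Assume baseline standing 114/72, pulse 88. On treatment: sitting 120/75, pulse 76, then standing 92/52, pulse 112.

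- Within-visit change: 120 − 92 = 28 mmHg fall, 75 − 52 = 23 mmHg fall, 112 − 76 = 36 bpm rise.
- Standing against its own baseline: 92 − 114 = −22, 52 − 72 = −20, 112 − 88 = +24. All three meet the change column.
- Limits: 92 is not < 90, 52 is not < 50, 112 is not > 120. No flag.
- The sitting values 120, 75 and 76 pass no limit, so they raise no flag whatever their baseline.

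**Step 2: when a systolic fall is missed although standing values are screened.** Let S be the sitting systolic value, F the fall, and assume the standing baseline equals S. For F of at least 20 the change condition is met, so the low flag needs S − F < 90. The fall is missed when S ≥ 90 + F.

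| Fall F (mmHg) | Missed when sitting systolic is at least |
|---|---|
| 20 | 110 |
| 25 | 115 |
| 30 | 120 |
| 40 | 130 |

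**Step 3: four more assumed children**, with standing pulse not above 115 and unremarkable sitting values.

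| Sitting → standing | Fall | Baseline standing | Sitting only | Standing also screened |
|---|---|---|---|---|
| 125/78 → 93/60 | 32/18 | 120/76 | no flag | no flag |
| 112/70 → 92/58 | 20/12 | 112/72 | no flag | no flag |
| 105/66 → 84/52 | 21/14 | 100/64 | no flag | no flag (100 − 84 = 16, below 20) |
| 108/66 → 84/52 | 24/14 | 106/68 | no flag | flagged as low systolic (84 < 90; 106 − 84 = 22) |

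With sitting values only, all four are missed. With standing values screened, three of four are missed and the fourth appears as low pressure. These are existence examples, not frequencies.

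**Step 4: how much paired data there is.** Scheduled clinic occasions for a child who stays to open-label Week 20: screening and baseline (2), open-label Weeks 1, 2, 4, 8, 12, 14, 16, 18, 20 (9), double-blind Weeks 1, 2, 4, 8, 12 (5). Total 2 + 9 + 5 = 16. Randomization at Week 14 drops three visits, giving 13. Converting the six remote visits (Weeks 3, 6 and 10 of each phase) to clinic visits would give 16 + 6 = 22.

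**Step 5: what means by position would recover.** If the same children contribute both readings, mean standing change minus mean sitting change equals the mean change in (standing − sitting). Tables by position would therefore show the average orthostatic effect. They would not count the children with a large fall.

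**The case against.** Several counter-arguments have force.

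- **Some falls would be caught.** If standing values are screened, a fall that ends below 90 systolic or 50 diastolic and is at least 20 or 15 mmHg below baseline is flagged. This stands. A reader might infer that every child with a large fall is counted as normal; the documents support only that such a child can be.
- **Means by position would show the average effect.** This also stands (Step 5). A reader might infer that the trial cannot say anything about orthostatic pressure. That goes too far: the data are collected, and correcting the SAP 9.4 positions and tabulating by position would give the average. It would not repair the incidence tables.
- **The vital-sign tables are not the only detection.** Investigators see the readings, and a symptomatic fall can be reported as an adverse event. The gap is in the tabulation.
- **No orthostatic endpoint is promised.** The endpoint is simply vital signs, the appendices attribute their limits to an external FDA draft, and the SAP is now descriptive. Leaving out the difference contradicts nothing. The supine/standing mismatch between SAP 9.4 and the protocol, however, is a contradiction.
- **The listings cannot be checked in full.** The SAP text available for review stops early in the patient data listings. A by-subject vital-sign listing may exist, but it would be neither a flag nor an incidence.

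**Conclusion.** The point holds in this form: an orthostatic pair is collected, no criterion, analysis or visible planned table uses the sitting-to-standing change, and SAP 9.4 misstates the positions. CT-11.2 and CT-17.2 can therefore report no abnormality for a child with a large fall on standing. With sitting values alone, a fall of any size is invisible. With standing values screened, and a standing baseline equal to the current sitting value, a 20 mmHg systolic fall is missed from a sitting systolic of 110 upward and a 30 mmHg fall from 120 upward.

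All readings used are assumed, and the documents give no basis for a frequency. No primary result or hypothesis test is affected. The consequence is an incomplete descriptive safety report on data already in hand.

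**What to change.** The change belongs in the SAP.

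1. Reconcile SAP 9.4 with the protocol's sitting and standing positions. State which position feeds each flag and each baseline, and apply the last-repeat rule within position. Present CT-11.1.1 and CT-17.1.1 by position, each against its own baseline.
2. Add the standing-minus-sitting difference in systolic pressure, diastolic pressure and heart rate to those two tables.
3. Add one orthostatic reporting row to SAP Appendix 2, with a cut-off the sponsor pre-specifies. The 20/15 mmHg magnitudes in Appendix 1 are one option, but they were set for change from baseline, so their use within a visit needs a stated reason. Count the row in CT-11.2 and CT-17.2 for all children, by arm where there are arms.

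Show that row by whether it was already present at trial baseline and at randomization. Do not drop children who met it at the phase baseline. SAP 5.2 takes the double-blind baseline from the last open-label visit, at Week 14 or later on aripiprazole, so exclusion would hide falls already present on open-label drug.

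This is a reporting flag, not a management rule. It needs no new measurement. The cost is one derived variable (for three measures), one extra row per incidence table, the added rows in the mean-change tables, and some children flagged by chance in all arms.
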